## 1. BACKGROUND

This Morbidity and Mortality Statistical Analysis Plan (SAP) supplement accompanies the main Statistical Analysis Plan (360050-001). Where applicable, the analyses defined in this Morbidity and Mortality SAP supplement supersedes the main SAP and the current Bayesian Adaptive Design Report (BADR). In particular; this SAP supplement describes the data analyses planned to demonstrate device benefit for the morbidity and mortality endpoint to support the M&M supplemental PMA (PMA-S) Submission.

After evaluating the pre-planned Expedited Phase data as defined in the main SAP, a large, important and clinically relevant population emerged. This population subgroup is characterized by having an NT-proBNP < 1600 pg/ml. This subgroup is the focus of this SAP supplement.

The M&M analyses will support a PMA-S submission for the following Indication for Use statement: The BAROSTIM NEO System is indicated for patients with heart failure. Heart failure is defined as: New York Heart Association (NYHA) functional Class III or Class II (who had a recent history of Class III), a left ventricular ejection fraction (LVEF)  $\leq$  35% and a NT-proBNP < 1600 pg/ml despite being treated with the appropriate heart failure guideline-directed medical therapy, excluding subjects eligible for Cardiac Resynchronization Therapy (CRT) according to AHA/ACC/ESC guidelines.

In Table 1 below, data that has already been analyzed (data as of 03OCT2018) in the Interim Data for the respective endpoint is called *interim data*. The prospective confirmatory data, which has yet to be accrued and/or analyzed for the respective endpoint, is called the *prospective data*. The **Subgroup** refers to subjects with a baseline NT-proBNP < 1600 pg/ml. This SAP describes the plans for analyzing the Final M&M data to support the M&M PMA-S Submission (last column in Table 1 below).

**Table 1: BeAT-HF PMA Submissions and Data Elements**

Data	Expedited PMA Submission Interim Dec 2018 / Prospective Apr 2019			PMA-S Submission*
	Interim Data (Submitted Dec 19, 2018)		Prospective Confirmatory Data	M&M
	All	Subgroup	Subgroup	Subgroup
6-Month				
MANCE	Interim data	Interim data	Interim + prospective data p	
6MHW	Interim data	Interim data	Prospective data	
QOL	Interim data	Interim data	Prospective data	
NT-proBNP	Interim data	Interim data	Interim + prospective data b	
M&M trending	Interim data		Interim + prospective data p	
Final M&M				Interim / prospective data p

\*Future M&M SAP supplement; p pooled; b borrowing

This SAP includes sample size justification for randomizing an additional 72 subjects prospectively that will contribute to an increased sample size for the final M&M data. Summary details on the M&M endpoint analysis, analysis populations and sample sizes can be found in Table 2 below.

Updated 22Dec2022: Due to COVID-19, randomizations were completed on July 29, 2020 with 59 additional prospective subjects randomized (13 less than the originally planned 72 additional subjects). Thus, the total analysis population for the M&M endpoint is 319 randomized subjects instead of 331 noted in Table 2 below. Note: Four were randomized to treatment but were never implanted, so the total randomized is n=323. Table 2 provides the original planned sample size numbers.

**Table 2: Original Endpoints Details (Updated 22Dec2022)**

Evidence	Endpoint	Hypothesis	Analysis Population
Final M&M	Rate of morbidity and mortality events	
Relative rate of events in treatment arm superior compared to rate of events in control arm
 
Success criteria: Z-value assessing treatment effect at pre-specified interim analysis greater than Hwang-Shih-DeCani group-sequential upper bound
 
Operating characteristics: type I error = 0.044 (one-sided) power = 0.860
 
Minimum observed relative reduction required: 28% (pooled data)
	
Prospective data: Subjects with
 
 
• NT-proBNP < 1600 at baseline
 
• Potential additional follow-up after 03OCT2018
 
 
Maximum sample size contributing additional data: N=241 subjects randomized prior to interim still under follow-up + 72 additional subjects to be randomized
 
Interim data: Subjects with
 
 
• NT-proBNP < 1600 at baseline
 
• Follow-up through 03OCT2018
 
 
Sample size N=249, Treatment=119, Control=130
 
All data:
 
 
• NT-proBNP < 1600 at baseline
 
• Any post-activation follow-up
 
 
N = 331 (Updated n=319) (241 interim & prospective, 72 prospective only (Updated n=59), 18 interim only)

## 2. MORBIDITY AND MORTALITY (M&M) ENDPOINT DETAILS

This section provides details for endpoints that contain morbidity and mortality data, particularly the cardiovascular (CV) mortality and heart failure (HF) morbidity endpoints. **All morbidity and mortality events are defined in the BeAT-HF Clinical Events Committee (CEC) Charter.**

To comprehensively measure the impact of Barostim therapy on mortality and heart failure morbidity, several definitions of heart failure morbidity will be evaluated. The inclusion of several definitions is necessary to evaluate the impact of COVID-19 on mortality, treatment for heart failure (both inside and outside the hospital/ER), and challenges with obtaining morbidity and mortality documentation from the institutions. Relevant Sensitivity Analysis (Section 4) and Supporting Morbidity and Mortality Analyses (Section 5) may be performed for each of these definitions, if appropriate.

The primary morbidity and mortality endpoint will be analyzed when a minimum of 320 events have been adjudicated. The events to be included in the M&M endpoint analyses are defined as follows:

- After the Clinical Event Committee (CEC) meeting in which the adjudication of the 320th event occurs (CEC 320 Meeting), the ENDPOINT CLOSING DATE is established. This ENDPOINT CLOSING DATE will be the latest hosp/ER admission or censoring event onset date across ALL events adjudicated up to and including all events adjudicated during the CEC 320 Meeting (may exceed 320).
- Events that occur before the ENDPOINT CLOSING DATE will be included in the M&M endpoint analyses.

The assumptions for the primary morbidity and mortality endpoint are described in Section 7.

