## 3. PRIMARY AND FOCUSED ENDPOINTS

### 3.1. Primary Endpoint: Rate of CV Mortality and HF Morbidity

#### 3.1.1. Rate of Cardiovascular Mortality and Heart Failure Morbidity

The objective is to demonstrate that treatment with the BAROSTIM NEO System, relative to medical management, reduces the rate of cardiovascular mortality or worsening heart failure that leads to hospitalization or emergency room visit, cardiac assist device or heart transplant.

Subjects will be censored at the time of a terminal event (i.e., death, permanent cardiac assist device, heart transplant, or novel implantation of a device to receive Cardiac Contractility Modulation) or end of follow-up, whichever occurs first.

The end of follow-up for analysis of morbidity and mortality will occur on the last date where adverse event status is known for the subject. This definition of follow-up time ensures that only time periods where morbidity and mortality status has

been assessed are included. End of follow-up is defined for each subject as the later date of:

- Last study visit
- Last date of adverse events reported in the database:
  - If last adverse event is a hospitalization, use discharge date
  - If last event is not a hospitalization, use resolution date if resolved, else use onset date
- Date subject completed the final, protocol defined end of study visit (note: this only occurs at end of study)

This end of follow-up date will be used to calculate follow-up time for the negative binomial model.

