### 3.1.3. Group sequential design

Morbidity and mortality will be evaluated using a frequentist group sequential design. The group sequential boundaries are specified by the Hwang-Shih-DeCani spending function with  $\gamma = -3$ . The parameter  $\gamma$  indexes the Hwang-Shih-DeCani spending function such that  $\gamma = -4$  is similar to an O'Brien-Fleming boundary and  $\gamma = 1$  is similar to a Pocock boundary. Analyses are planned based on data accumulated through the time at which 140, 180, 240, and 320 primary endpoint events have occurred in the trial. These three interim analyses and a final analysis after 320 events have occurred are planned due to uncertainty regarding the treatment effect size. A large treatment effect would result in stopping the study at one of the interim analyses while a more moderate treatment effect would require more events in order to conclude that the treatment effect is statistically significant.

The boundaries of the Hwang-Shih-DeCani spending function at each interim analysis will be determined based on the estimated information fraction at the time of analysis and at any previous interim analyses. The information fraction for a negative binomial model estimate of the treatment effect comparing two randomized arms is defined in Mütze et al. (2018). The information fraction depends on the event rate in each arm, the length of follow-up of each patient, and the variance (dispersion) of the negative binomial distribution. A consistent estimate of the information can be obtained by plugging in maximum likelihood estimates from the interim data. At each interim analysis, the total information of the trial at 320 events will be estimated based on simulation through 320 events using the negative binomial model parameter estimates (e.g., dispersion) obtained at the time of interim analysis. The estimated information at the time of the interim analysis divided by the simulated total information at 320 events will provide the information fraction at the interim analysis to determine the spending function boundary.

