## 5.2. M&M endpoints with follow-up ending at 6, 12 and 24 months

Over the course of follow-up in the trial, there were many unexpected changes that occurred in patient care that could confound the evaluation of the benefit of Barostim therapy. These include the approval and adoption of pharmaceutical and device-based treatments for heart failure (e.g., ARNI, SGLT2, Cardiac Contractility Modulation), as well as changes in care patterns and practices due to COVID-19. To better understand the impact of these event, the analyses on the morbidity and mortality endpoints will be repeated assuming that follow-up stops at 6 months, 12 months and 24 months. The same endpoint definitions as described above and analysis methods in Section 2.1.4 will be repeated while censoring follow-up time and events at 6, 12, and 24 months.

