A stratified analysis, using the negative binomial model as specified in the primary analysis, may also be performed to further evaluate any difference in treatment effect pre-March 13, 2020, versus post-March 13, 2020. Separate estimates of the treatment effect will be made with data pre-March 13, 2020, and post-March 13, 2020. The follow-up time for the first model will be censored on March 12, 2020, while the follow-up start time for the second model will be March 13, 2020. The Anderson-Gill method for recurrent events model may also be used along with a time-varying covariate for follow-up pre- and post- March 13, 2020. The significance of the time-varying covariate as well as the interaction with treatment group would be reported. As with the negative binomial model, a p-value for the interaction term less than 0.15 will be considered evidence of a significant interaction between the treatment effect pre COVID-19 vs post COVID-19.

If there is evidence that the treatment effect is different pre- vs post-March 13, 2020, then the benefit observed pre-March 13, 2020 would be more consistent with the assumptions and definitions of the study endpoints. This includes the definition and assumed event rate for heart failure hospitalization, as it has been observed that patients have shown a reluctance to interact with the health care setting during the COVID-19 pandemic, some by reducing their risk of hospitalization by changing their behaviors and others by receiving care remotely to replace what may have previously been a hospitalization (e.g. acute medication changes).

In addition to the analyses specified above, other additional relevant information will be considered, such as:

- Number and percent of pre- vs post- March 2020 information (events, follow-up time, rate)
- Follow-up visit compliance pre- vs post- March 2020
- Comparison of other definitions of heart failure on event rates between treatment arms pre- vs post- March 2020, such as
  - Expanded definition of heart failure (see CEC Charter)
  - Unscheduled clinic visits

- Acute changes in medications
- Evaluate the impact using the responses on the COVID-19 case report form. This includes summarizing, or incorporating in the analyses, the instances where subjects reported the need to go to an emergency department or hospital for their heart failure but decided not to because of concerns about COVID-19.

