- Evaluate the information regarding the CEC determined impact of COVID-19 on events, such as HF hospitalizations where CEC determined the event was a study endpoint, but COVID-19 was considered a “Co-primary” or a contributing factor, or where COVID-19 was the primary reason for hospitalization, but heart failure was the secondary reason.
- Evaluate all COVID related adverse events and deaths
- Evaluate COVID related deviation and the impact on the trial and results

There are three interim analyses schedule at approximately 140 (44%, Jan 2020), 180 (~56%, Oct 2020), 240 (~75%, Oct 2021) primary endpoint events, and a final at ~320 events (100%, TBD). Thus, the first and possibly much of the second interim analyses primarily include data that were not impacted by COVID-19. As such, these analyses may also provide insight into the impact of COVID-19 and will be provided in the PMA Supplement submission.

The totality of evidence available will be considered when evaluating the impact of COVID. This includes all evidence of a differential treatment effect of Barostim therapy pre- vs. post-March 13. This includes, at a minimum, the analyses specified above as well as the qualitative assessments of the impact of the COVID-19 pandemic on the study based on the relevant information collected above.

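### Primary events stop counting at the endpoint closing date, but the follow-up time in the negative binomial offset does not stop there

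*SAP*

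**What the plan says.** **Numerator.** SAP section 2 fixes the closing date after the committee meeting that adjudicates the 320th event: "This ENDPOINT CLOSING DATE will be the latest hosp/ER admission or censoring event onset date across ALL events adjudicated", up to and including that meeting. It then states: "Events that occur before the ENDPOINT CLOSING DATE will be included in the M&M endpoint analyses".

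**Denominator.** SAP 3.1.1 censors at a terminal event or at end of follow-up, whichever comes first. End of follow-up is the latest of the last study visit, the last adverse-event date and a third anchor: "Date subject completed the final, protocol defined end of study visit (note: this only occurs at end of study)". It adds: "This end of follow-up date will be used to calculate follow-up time for the negative binomial model". SAP 3.1.4 enters the log of that time as the offset.

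The closing date does not appear in SAP 3.1.1, 3.1.4 or 3.1.5, or in Protocol 4.3.1. It is mentioned again only in SAP 3.2.1, which allows the expanded-definition analysis to add later events.

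**The concern.** A rate needs its events and its exposure taken over the same window. Here the two windows are set by different rules. A programmer following the SAP would add patient-time after the closing date to the offset and discard any events in that time. This also defeats the stated aim of 3.1.1, which is to include only time in which morbidity and mortality status was assessed.

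Events per patient-year would be too low in both arms. The rate ratio, and so the primary Z-statistic, would depend on how much post-closing time each arm happens to have. These analyses support a PMA supplement (SAP 1). The focused analyses in 3.2.1 and 3.2.3, which SAP 3.2 ties to labeling, are modelled on the primary analysis and reuse its follow-up definition.

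The word *before* is a separate slip: read strictly, it excludes any event on the closing date, including the event that sets it.

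**Working it through.** **1. Is there a cap elsewhere?** SAP 3.1.3 comes nearest: "Analyses are planned based on data accumulated through the time at which 140, 180, 240, and 320 primary endpoint events have occurred". That suggests a data cut, but it is tied to events having occurred, whereas the closing date depends on adjudication, and it does not redefine follow-up. Where the SAP wants exposure cut, it says so. Section 5.2 analyses "will be repeated while censoring follow-up time and events at 6, 12, and 24 months", and section 7 states: "The follow-up time for the first model will be censored on March 12, 2020".

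**2. Can subjects have follow-up after the closing date?** The closing date is a past onset date known only after the meeting, so visits cannot be timed to it. SAP section 7 gives "180 (~56%, Oct 2020), 240 (~75%, Oct 2021) primary endpoint events".
- 240 − 180 = 60 events in 12 months, or 5 per month. The last 80 events then take 80/5 = 16 months, to about February 2023.
- The last randomization was 29 July 2020 (SAP 1), so by then all subjects are past 24 months and on visits every 180 ± 60 days (Protocol Table 6).
- The next visit falls on average 90 days (0.25 year) after closing, and at most 240 days (0.66 year).

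An end-of-study visit could be later, so I use 0.25 to 1.0 year as an assumed range.

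**3. Scale of the test.** The 86.0% conditional power in SAP 8.1 depends on patient-level data to 3 October 2018 and cannot be reproduced from the documents. The boundaries can. A Hwang-Shih-DeCani function (γ = −3, α = 0.01), with information fractions backed out of the alpha spent in Table 7, gives 2.894, 2.879, 2.671 and 2.433, against 2.9032, 2.8781, 2.6713 and 2.4335 stated. The 28% minimum reduction in Table 2 implies SE(log RR) = −ln(0.72)/2.4335 = 0.135; the simulation below gives 0.142–0.144.

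**4. Absolute rates.** With T the mean follow-up to closing, a the fraction still active then and g the gap, the rate is multiplied by T/(T + a·g).

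- *Inputs from the SAP:* control rate 0.4 per patient-year, rate ratio 0.65, terminal probability 0.18 and dispersion 1.7 (8.1); 319 subjects (1); about 320 events. I read 1.7 as a gamma shape, because Table 4 labels the lower value 1.4 as larger overdispersion.
- *Assumed:* entry over 4 years; 0% or 15% withdrawal before closing, the same in both arms; prior-hospitalization covariate omitted.

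Each of 3,000–4,000 simulated trials per scenario was fitted twice, once with the offset capped at closing and once with it running on by g. Events were counted to closing in both fits.

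| Gap g (years) | Control rate understated, true RR 0.65 | RR factor, true RR 0.65 | RR factor, null |
|---|---|---|---|
| 0.25 | about 5% | 0.995 | 1.000 |
| 0.66 | 12–14% | 0.987 | 1.000 |
| 1.0 | 17–19% | 0.980 | 1.000 |

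A separate simulation (400 trials per scenario) had T = 3.13 years over both arms, rising to 3.33 at g = 0.25 and 3.93 at g = 1.0. The formula gives 3.13/3.33 = 0.940 and 3.13/3.93 = 0.796. The control rate fell from 0.374 to 0.351 (6.1%) and 0.298 (20.3%). Under the null it fell from 0.376 to 0.348 (7.4%) and 0.286 (23.9%).

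**5. Rate ratio with equal gaps.** Under a true effect the device arm has fewer terminal events, so more of it is active at closing (85% against 78%; 71% against 65% with withdrawals) and it gains more uncounted time. At worst 0.650 becomes 0.650 × 0.980 = 0.637. On the log scale that is −ln(0.980) = 0.0202, or 0.0202/0.135 = 0.15 SE. Z moves by only 0.01–0.04, because the SE also grows. In the separate simulation, ln(0.6517)/3.019 gives an SE of about 0.142 when capped, and ln(0.6385)/3.059 gives about 0.147 at g = 1.0.

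**6. Rate ratio with unequal gaps (hypothetical), under the null.** A 0.1-year difference gives a factor of 0.974–0.978 or 1.022–1.027, which is 0.15–0.19 in Z. A 0.25-year difference (0.25 against 0.5) gives 0.938–0.948 or 1.055–1.066, which is 0.37–0.45 in Z. The arm with more post-closing time is favoured.

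**7. The word *before*.** If exactly 320 endpoint events are adjudicated and the latest one sets the date, at most 320 − 1 = 319 are analysed.

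**The case against.** The best case is that a common cut is plainly intended. SAP 3.1.3 refers to data, not just events; SAP 8.1 simulates follow-up and events together through 320 events; and 3.1.1 wants only assessed time. The supplement also accompanies a main SAP that is not available here and might contain a cut. This supports intent, but it does not alter the explicit follow-up rule in 3.1.1, and section 8.1 describes simulations rather than the analysis.

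The size can also be challenged, and much of that stands:
- The gap is assumed. No snapshot or lock date is given, and for subjects with no contact after closing the cap would change nothing.
- Uniform 4-year entry puts closing about 1.65 years after last entry, earlier than the February 2023 anchor implies. Moving it to 2.55 years, with the control rate lowered to 0.30–0.33 to keep about 320 events, gives understatement of about 4.7%, 11.5% and 16.5% at the three gaps, slightly smaller than tabulated.
- The larger Z shifts need unequal gaps, while Protocol 3.1 plans identical follow-up in both arms.
- No passage says absolute rates will appear in labeling; the primary effect is a relative reduction.
- The *before* wording costs an event only in a narrow case. More than 320 events may be adjudicated, and an adjudicated event that is not an endpoint event could set the date.

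**Conclusion.** The inconsistency is real: SAP section 2 cuts events at the closing date and 3.1.1 does not cut the exposure. Across the simulations the control rate is understated by about 5–7% at a 0.25-year gap and 17–24% at 1.0 year. With equal gaps there is no inflation of the rate ratio under the null, and the gain for the device under a true 35% reduction is negligible on the Z scale. A material effect on the primary test requires post-closing time to differ by arm. That is possible but not predicted by the documents, and its direction is unknown. All sizes rest on the assumed gap, entry pattern and withdrawal. The point should be fixed because the primary test need not depend on post-closing visit timing, and the cut should not be chosen with results in view.

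**What to change.** - **SAP 3.1.1:** state that, for the primary model, follow-up ends at the earliest of terminal event, end of follow-up as now defined, and the endpoint closing date.
- **SAP 2:** count events *on or before* the closing date.
- **SAP 3.2.1:** if events after the closing date are added, define the later cut date and apply it to both events and follow-up in that analysis.
- If the main SAP already contains such a cap, cross-refer to it in 3.1.1.

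The cost is one or two sentences and one line of code, with no new data. It should be settled before the treatment comparison is run.

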## 3. PRIMARY AND FOCUSED ENDPOINTS

### 3.1. Primary Endpoint: Rate of CV Mortality and HF Morbidity

#### 3.1.1. Rate of Cardiovascular Mortality and Heart Failure Morbidity

The objective is to demonstrate that treatment with the BAROSTIM NEO System, relative to medical management, reduces the rate of cardiovascular mortality or worsening heart failure that leads to hospitalization or emergency room visit, cardiac assist device or heart transplant.

Subjects will be censored at the time of a terminal event (i.e., death, permanent cardiac assist device, heart transplant, or novel implantation of a device to receive Cardiac Contractility Modulation) or end of follow-up, whichever occurs first.

The end of follow-up for analysis of morbidity and mortality will occur on the last date where adverse event status is known for the subject. This definition of follow-up time ensures that only time periods where morbidity and mortality status has

been assessed are included. End of follow-up is defined for each subject as the later date of:

- Last study visit
- Last date of adverse events reported in the database:
  - If last adverse event is a hospitalization, use discharge date
  - If last event is not a hospitalization, use resolution date if resolved, else use onset date
- Date subject completed the final, protocol defined end of study visit (note: this only occurs at end of study)

This end of follow-up date will be used to calculate follow-up time for the negative binomial model.

